4.2 Adherence and protocol deviations

Potential protocol deviations and violations are reported to the Coordinating Centre within 72 hours and further classified into four categories (figure below), reflecting the following situations wherein: (1) an RBC transfusion occurred while the Hb threshold is not reached, (2) more than one unit is transfused without reassessing the Hb level between transfusions, (3) the delay between reaching the transfusion threshold and transfusion is greater than 3 hours or a transfusion never occurred despite reaching the transfusion threshold and (4) no transfusion occurred in the context of life-sustaining therapy withdrawal. Using a standard operating procedure detailed in the Study Protocol version 3.0, an adjudication committee will determine whether each reported event represents a protocol violation, a protocol deviation or neither.

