4.3 Analysis populations

Intention-to-treat population. This population includes all randomized TBI patients except those who withdrew consent or were lost to follow-up. Baseline characteristics for the intention-to-treat population will be reported in the main manuscript.

Per-protocol population: This population includes all patients within the intention-to-treat group, except those who were allocated to the liberal strategy but were not transfused within a 24-hour time window after reaching Hb ≤ 100 g/L (protocol violation category #3), and those who were allocated to the restrictive strategy but were transfused despite not reaching their transfusion threshold of ≤ 70 g/L, or received more than one unit without reassessing the Hb despite the absence of ongoing important bleeding (protocol violation category #1 and 2). Baseline characteristics for the per-protocol population will be reported in an online Supplementary Appendix.

For the patients included and excluded from the per-protocol population, the median time to transfusion and the mean pretransfusion Hb level will be reported according to the treatment allocation.

Section 5 – Trial Population

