Mortality in the ICU, in the hospital and at 6 months	
 Frailty model¶ 	
 Complete case analysis** 	
 Unadjusted models 	-
FIM (total score, motor and cognition sub-scores)	
 Linear mixed model¶ 	
 Complete case analysis** 	
 Unadjusted models 	-
EQ VAS	
 Linear mixed model¶ 	
 Complete case analysis** 	
 Unadjusted models 	-
QOLIBRI	
 Linear mixed model¶ 	
 Complete case analysis** 	
 Unadjusted models 	-
PHQ-9	
 Linear mixed model¶ Robust hierarchical Poisson regression¶, with a dichotomized PHQ-9 at ≥ 10. 	
 Complete case analysis** 	
 Unadjusted models 	-
Tertiary outcomes				
Number of RBC units transfused per patient in the ICU	Student's t-test		-	-
Lowest daily Hb	Graphically displayed with 95% at each time point		-	-
Infections and transfusion complications	Chi-square test		-	-
Duration of mechanical ventilation	Wilcoxon rank sum test		-	-
Length of stay in the ICU and in the hospital	Wilcoxon rank sum test		-	-

* Adjusted for sex

† Includes only patients for whom no covariate was imputed using conditional estimation to calculate the TBI-IMPACT prognostic score

‡ This population includes all patients within the intention-to-treat group, except those who were allocated to the liberal strategy but were not transfused within a 24-hour time window after reaching Hb ≤ 100 g/L, and those who were allocated to the restrictive strategy but were transfused despite not reaching their transfusion threshold of ≤ 70 g/L, or received more than one unit without reassessing the Hb despite the absence of ongoing important bleeding.

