* The Glasgow Outcome Scale extended (GOSe), measured at 6-month, comprises eight ranking levels from 1 (death, least favourable outcome) to 8 (upper good recovery, most favourable outcome). The primary outcome was centrally assessed by blinded trained personnel.

† The treatment effect is a risk ratio unless otherwise indicated. Confidence intervals have not been adjusted for multiplicity, and inferences drawn from the intervals may not be reproducible.

‡ According to a sliding dichotomy of the GOSe. The sliding dichotomy approach is based on International Mission for Prognosis and Analysis of Clinical Trials in TBI (TBI-IMPACT) Core+CT+Lab prognostic model, which includes admission characteristics (age, motor score, pupils, hypoxemia, hypotension, CT classification, traumatic tSAH on CT, epidural mass on CT, glycemia and Hb). When necessary, we used conditional estimation for missing covariates to calculate an individual TBI-IMPACT score for each patient. Patients will be split into 3 tertiles based on their predicted risk of unfavourable outcome (mortality/vegetative state/severe disability) at 6 months. Patients categorized in the low-risk group will be considered to have an unfavourable outcome if the 6-month GOSe is ≤ 5 (i.e., death, vegetative state, lower and severe disability, or lower moderate disability). Patients in the intermediate risk group will be considered to have an unfavourable outcome if the 6-month GOSe is ≤ 4 (i.e., death, vegetative state, or lower and severe disability). Patients in the high-risk group will be considered to have an unfavourable outcome if the 6-month GOSe is ≤ 3 (i.e., death, vegetative state or lower severe disability). Analyses are adjusted for sex, with a random intercept for site.

§ The complete case analysis includes only patients for whom no covariate to calculate the TBI-IMPACT prognostic score was imputed using conditional estimation.

¶ The per protocol analysis excludes patients who were allocated to the liberal strategy but were not transfused within a 24-hour time window after reaching Hb ≤ 100 g/L, and those who were allocated to the restrictive strategy but were transfused despite not reaching the transfusion threshold of ≤ 70 g/L or received more than one unit without reassessing the Hb despite the absence of ongoing important bleeding.

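### Do the Table 1 and Appendix 2 footnotes define a different per-protocol population from SAP section 4.3?

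*SAP*

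**What the plan says.** Section 4.2 sorts reported events into four categories. Category 3 covers late transfusion and also the case where "a transfusion never occurred despite reaching the transfusion threshold". Category 4 is separate: "4) no transfusion occurred in the context of life-sustaining therapy withdrawal". The section adds that "an adjudication committee will determine whether each reported event represents a protocol violation, a protocol deviation or neither", under a procedure held in protocol version 3.0.

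Section 4.3 starts the per-protocol population from the intention-to-treat population and removes two groups:

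- liberal-arm patients who "were not transfused within a 24-hour time window after reaching Hb ≤ 100 g/L (protocol violation category #3");
- restrictive-arm patients transfused above their threshold, or given more than one unit without a repeat Hb "despite the absence of ongoing important bleeding (protocol violation category #1 and 2").

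Table 1 footnote ‡ gives the same exclusions, but its liberal-arm clause runs straight on with no label: "were not transfused within a 24-hour time window after reaching Hb ≤ 100 g/L, and those who were allocated to the restrictive strategy". Appendix 2 Table 2 footnote ¶ does the same: "The per protocol analysis excludes patients who were allocated to the liberal strategy but were not transfused within a 24-hour time window". For the restrictive arm it ends with those who "received more than one unit without reassessing the Hb despite the absence of ongoing important bleeding", again unlabelled.

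Section 6.2.1.2 lists the per-protocol analysis as a sensitivity analysis of the primary outcome and, for its definition, refers only to section 4.3. Section 6.2 says the analyses are summarised in Table 1 and reported in the layout of Appendix 2.

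**The concern.** A per-protocol set is defined by events after randomisation, so small differences in wording can change who is in it. If the labels in section 4.3 act as limits, only adjudicated violations in the named categories lead to exclusion, and category 4 patients stay in. The footnotes carry no such limit. Taken alone, they differ in two ways:

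- They would remove a liberal-arm patient who was not transfused because life-sustaining therapy was being withdrawn. The restrictive-arm wording concerns only transfusions that were given, so a comparable untransfused restrictive-arm patient would stay.
- They would remove patients whose event met the description but was adjudicated a deviation or neither.

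The first difference could bias the comparison. Many such patients would be expected to die, and death is unfavourable in all three prognostic tertiles (section 6.1.1; even the lowest cut, GOSe ≤ 3, includes it). Each such death removed takes an unfavourable outcome from the liberal arm only. The published table could also describe a set other than the one analysed.

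A related question concerns section 4.3 itself: could a liberal-arm patient who dies untransfused inside the 24-hour window count as a category 3 event and be excluded?

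**Working it through.** **The definitions side by side**

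| Element | Section 4.3 | Table 1 ‡ | Appendix 2 Table 2 ¶ |
|---|---|---|---|
| Liberal arm: 24-hour window from Hb ≤ 100 g/L | yes | yes | yes |
| Restrictive arm: transfused above 70 g/L | yes | yes | yes |
| Restrictive arm: more than one unit without repeat Hb, bleeding qualifier | yes | yes | yes |
| Label: violation category 3 (liberal) | yes | no | no |
| Label: violation categories 1 and 2 (restrictive) | yes | no | no |
| Category 4 mentioned | no | no | no |

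Every substantive criterion agrees. Only the labels differ, and they can be read in two ways.

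- *As limits.* Section 4.3 is then narrower than the footnotes. Section 6.2.1.2 points to section 4.3, so the narrower set is the one analysed.
- *As cross-references* naming the category each described event belongs to. Section 4.3 and the footnotes then define the same set.

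On neither reading do the footnotes produce a different analysed set.

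**The plan's own figures**

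Inputs from section 3.3: risks 40% and 30%, two-sided 5%, power 80%. Mean risk = 0.35.

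n per arm = [1.96·√(2·0.35·0.65) + 0.8416·√(0.40·0.60 + 0.30·0.70)]² / 0.10² = (1.322 + 0.565)² / 0.01 ≈ 356, so 712 in total. With the dropout formula of section 3.5, 712/0.98² = 741.4, raised to 742. Both stated figures reproduce.

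**Illustration of the first difference**

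Assumptions: no true effect; 40% unfavourable in both arms (the section 3.3 control risk for GOSe ≤ 4, standing in for the sliding dichotomy); 742 × 0.98 / 2 = 363.6, taken as 364 per arm; all k extra liberal exclusions unfavourable. The counts k are assumed, as the SAP gives none.

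Liberal risk = (0.40 × 364 − k) / (364 − k); RR = liberal risk / 0.40.

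| k | Share of arm | Liberal risk | RR |
|---|---|---|---|
| 1 | 0.3% | 144.6/363 = 0.3983 | 0.996 |
| 4 | 1.1% | 141.6/360 = 0.3933 | 0.983 |
| 7 | 1.9% | 138.6/357 = 0.3882 | 0.971 |
| 12 | 3.3% | 133.6/352 = 0.3795 | 0.949 |
| 20 | 5.5% | 125.6/344 = 0.3651 | 0.913 |

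Reaching RR 0.95 takes k = (145.6 − 0.38 × 364)/0.62 = 11.7, about 12 patients.

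For scale, ignoring adjustment and site, the standard error of log RR at these inputs is √(2 × 0.60/145.6) = 0.091. A 95% interval around RR 1.00 then runs from about 0.84 to 1.19.

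**Adding the second difference**

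Suppose 7 restrictive-arm patients are also removed, at an assumed 60% or 80% risk. The restrictive risk becomes (145.6 − 4.2)/357 = 0.3961 or (145.6 − 5.6)/357 = 0.3922. With 4 liberal exclusions, RR = 0.993 or 1.003. With 7, RR = 0.980 or 0.990. The shift shrinks, and in one case changes sign.

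These figures start from the full intention-to-treat set and model the second difference in the restrictive arm only. They show scale and do not measure section 4.3 against the footnotes.

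**The case for a change.** The strongest case for a change is that footnote ‡ is phrased as a complete definition of the population, and that section 6.2 ties reporting to Appendix 2. Version 1.1 of the SAP also revised the Table 1 legend to match clarified text, so the sponsor has treated such legends as worth aligning. Category 4 is a real prospect: section 5.1 excludes decisions to withhold or withdraw life-sustaining therapy only when made by screening, and section 6.2 cites regional variation in stopping such therapy as a reason to adjust for site. And if the labels are mere cross-references, section 4.3 does not settle category 4 either, because the never-transfused part of category 3 literally overlaps it.

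The footnotes are indeed incomplete, and a reader who saw only the results table could misread the set. The overlap between categories 3 and 4 is also present in the visible text. But where that line falls, and what becomes of a patient who dies inside the window, are matters for the adjudication procedure. That procedure sits in the protocol, which is not shown, and section 4.2 refers to a figure of the categories that is also missing from the text reviewed. Their absence here cannot be counted as a gap in the plan. A new sentence on category 4 and early death might restate an existing rule or conflict with one.

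The second difference is narrower than it first appears. All three definitions keep the 24-hour window and the bleeding qualifier, so a delay of 3 to 24 hours is excluded by none of them. It reaches only events that meet those criteria yet were not graded violations. Nor do the footnotes create the arm asymmetry: section 4.3 already applies different event types to the two arms.

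**Conclusion.** No change to the plan is needed. The footnotes drop the category labels, which is a clerical slip in copies of a definition whose governing text is identified: section 6.2.1.2 names section 4.3. An analyst following the SAP builds the section 4.3 set from adjudicated events, and restoring the labels would alter no result.

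The possible effect is confined to one of several sensitivity analyses of the primary outcome. The intention-to-treat main analysis is unaffected and no stated figure is wrong. Even if the footnotes were followed literally, the illustration gives RR 0.996 to 0.971 for 1 to 7 extra liberal exclusions, and about 12 (3.3% of the arm) are needed to reach 0.95. Those values assume 364 per arm, 40% risk, no true effect, every excluded patient unfavourable and no offset in the restrictive arm. The counts are not in the document, and with an offset the direction is unknown.

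Readers will also be able to see what was removed. The Appendix 2 results table shows per-protocol denominators by arm. Section 4.3 commits to reporting baseline characteristics for the set, and time to transfusion and pretransfusion Hb by allocation for patients included and excluded.

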5.1 Eligibility

Inclusion Criteria:

Subjects must meet all inclusion criteria to participate in this study.

- Adult patients (≥ 18 years old).
- Admitted to the ICU with an acute (hospital admission within 24 hours of injury) moderate or severe (Glasgow Coma Score [GCS] ≤ 12) blunt TBI.
- Hb level ≤ 100 g/L.

Exclusion Criteria

Subjects meeting any of the exclusion criteria are excluded from study participation.

- Receive transfusion after ICU admission.
- Have contraindications or known objection to transfusions.
- Have no fixed address.
- Patients who meet the criteria for neurological determination of death.
- Those with a GCS of 3 in combination with bilateral fixed dilated pupils at the time of randomization.
- Those with active life-threatening bleeding associated with hemorrhagic shock at the time of randomization.
- Patients for whom a decision to withhold or withdraw life-sustaining therapies has been made at the time of screening.

5.2 Withdrawal/Follow-up

The loss to follow-up rate is expected to be very low⁹. When a patient is lost to follow-up, the 6-month GOSe will be missing, therefore, this patient cannot be included in the analysis of the primary outcome. Whenever possible, such patients will be included in the secondary and tertiary outcome analyses.

No data will be analyzed for patients who withdraw consent, but such patients will be listed in the CONSORT diagram.

5.3 Baseline Patient Characteristics

Baseline characteristics that will be reported are detailed in [Appendix 2](#). To optimize the presentation of categorical variables, categories with less than 5% participant proportion will be merged with the next adjacent category. Further characteristics may be included, and adjustments can be made to the report format in order to meet editorial guidelines.

Section 6 – Analysis

6.1 Outcome Definitions

6.1.1 Primary outcome

- A sliding dichotomy of the GOSe will be used to assess neurological outcome at 6 months¹⁰. The GOSe comprises eight ranking levels from 1 (death, least favourable outcome) to 8 (upper good recovery, most favourable outcome)³. The sliding dichotomy approach will be based on the International Mission for Prognosis and Analysis of Clinical Trials in TBI (TBI-IMPACT) Core+CT+Lab prognostic model¹¹, which includes the following admission characteristics: age, motor score, pupils, hypoxemia, hypotension, computed tomography (CT) scan classification as defined on the Marshall scale¹², traumatic subarachnoid hemorrhage (tSAH) and epidural mass on head CT scan¹³, glycemia and Hb. Head CT scans results will be adjudicated centrally, using the worst results within the first 24 hours following the injury (see [Appendix 3](#)). For the motor score, we will use the score at emergency department discharge or the score prior to intubation when the patient was intubated in the emergency department. If no motor score was recorded in the emergency department, we will use the first score recorded upon hospital admission, as recommended¹⁴. Hypoxemia and hypotension were recorded in the emergency department, using standardized definitions⁴. For glycemia or Hb, we will use the worst value recorded in the emergency department and, when unavailable, the worst value recorded upon admission. Our approach to handling missing data is outlined in section 6.3.

Patients will then be split into 3 tertiles based on their predicted risk of unfavourable outcome (mortality/vegetative state/severe disability) at 6 months. Patients categorized in the low-risk group will be considered to have an unfavourable outcome if the 6-month GOSe is ≤ 5 (i.e., death, vegetative state, lower and severe disability, or lower moderate disability). Patients in the intermediate risk group will be considered to have an unfavourable outcome if the 6-month GOSe is ≤ 4 (i.e., death, vegetative state, or lower and severe disability). Patients in the high-risk group will be considered to have an unfavourable outcome if the 6-month GOSe is ≤ 3 (i.e., death, vegetative state or lower severe disability).

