3.1 Trial Design

HEMOTION is a pragmatic, parallel group, multi-centre, open label blinded-endpoint, randomized trial⁴. Once reaching a Hb ≤ 100 g/L and after a site investigator has confirmed eligibility, participants will be randomly allocated to either a liberal (experimental) or a restrictive (control) RBC transfusion strategy. The trial intervention is initiated within 3 hours in patients meeting the threshold for transfusion in their respective group. All primary and secondary outcomes are assessed centrally by trained research personnel blinded to the intervention to minimize the risk of bias during data collection. Tertiary outcomes are assessed at participating sites, unblinded to the intervention but using standardized definitions.

The control strategy: Patients in the restrictive transfusion strategy group receive an RBC transfusion only if their Hb is ≤ 70 g/L.

The experimental strategy: Patients in the liberal transfusion strategy group receive an RBC transfusion if their Hb is ≤ 100 g/L. This threshold, shown to be effective in maintaining adequate cerebral oxygenation, is considered acceptable by clinicians caring for critically ill patients with neurological injuries.

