§ GCS motor score of 1 indicates that the patient makes no movements to painful stimuli, 2 has extension, 3 has abnormal flexion, 4 has normal flexion, 5 localizes to painful stimuli, and 6 obeys commands.

¶ Hypotension was defined as a systolic blood pressure of less than 90 mm Hg.

|| Hypoxemia was defined as an arterial or pulse oxygen saturation of less than 90%.

** The Marshall classification is based on a review of the worst head computerized tomography (CT) scans results within the first 24 hours following the injury, with a score of I indicating normal findings, II indicating diffuse injury, III or IV indicating radiologic signs of elevated intracranial pressure, and V or VI indicating a mass lesion greater than 25 mL.

†† IMPACT-TBI prognosis model is validated to predict functional outcome (Glasgow Outcome Scale Extended < 4) of patients with traumatic brain injury and a GCS score < 13. It is adjusted for age, GCS motor score, pupil response, hypoxia, hypotension, CT classification, blood glucose and hemoglobin concentrations upon admission.

Table 2. Analyses of the Primary Outcome.*

	Liberal Strategy (N = xxx)	Restrictive Strategy (N = yyy)	Treatment Effect (95% CI)†
Main Analysis — no./total no. (%)			
Sliding dichotomy for unfavorable outcome‡			
Overall	xxx/xxx (xx.x)	yyy/yyy (yy.y)	x.xx (y.yy to z.zz)
Worst predicted prognosis group			—
Intermediate predicted prognosis group			—
Best predicted prognosis group			—
Sensitivity Analyses			
Sliding dichotomy for unfavorable outcome‡			
Complete case analysis§ — no./total no. (%)			x.xx (y.yy to z.zz)
Per protocol analysis¶ — no./total no. (%)			x.xx (y.yy to z.zz)
Best case scenario — no./total no. (%)			x.xx (y.yy to z.zz)
Worst case scenario** — no./total no. (%)			x.xx (y.yy to z.zz)
Additional Analyses			
Hierarchical proportional odds analysis††			x.xx (y.yy to z.zz)
Death — no./total no. (%)			—
Vegetative state — no./total no. (%)			—
Lower severe disability — no./total no. (%)			—
Upper severe disability — no./total no. (%)			—
Lower moderate disability — no./total no. (%)			—
Upper moderate disability — no./total no. (%)			—
Lower good recovery — no./total no. (%)			—
Upper good recovery — no./total no. (%)			—
Dichotomized unfavorable outcome‡‡			
Robust hierarchical Poisson regression§§			x.xx (y.yy to z.zz)
Chi-square test			x.xx (y.yy to z.zz)

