Initially, each head CT scan was interpreted by radiologists at participating sites who were unrelated to the research team and unaware of group assignment and clinical outcome of study participants. Subsequent to this interpretation, the local investigator interpreted the CT scan to calculate the Marshall score¹², the Rotterdam score¹³ including the presence or absence of epidural hematoma and subarachnoid hemorrhage. The local research team transmitted this information to the coordinating centre.

Given that the local research teams were unblinded to transfusion strategies, all CT reports underwent a second independent analysis by an investigator blinded to group assignment and trial outcomes.

A third adjudication was performed by a second investigator also blinded to the group assignment and trial outcomes. All discrepant interpretations between the site investigator reading and the central adjudication were reviewed independently. If needed, local research teams and the first adjudicator were consulted for clarification. The third adjudication serving as the final decision.

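### The CT window that helps set each patient's primary-outcome cut-off is counted from injury and not closed at randomisation, so a post-randomisation scan could set the cut-off; the likely bias is small and the rule is cheap to tighten.

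*SAP*

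**What the plan says.** Section 6.1.1 builds the sliding dichotomy on the IMPACT Core+CT+Lab model, "which includes the following admission characteristics". Motor score, hypoxaemia, hypotension, glucose and haemoglobin are tied to the emergency department or, failing that for motor score, glucose and haemoglobin, to admission. The CT items are centrally adjudicated, "using the worst results within the first 24 hours following the injury". The footnote to the baseline table in Appendix 2 repeats the window: "The Marshall classification is based on a review of the worst head computerized tomography (CT) scans results within the first 24 hours" after injury. Appendix 3 describes how scans are read and adds no time limit.

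The score then fixes the endpoint: "Patients will then be split into 3 tertiles based on their predicted risk of unfavourable outcome". Unfavourable means GOSe ≤5 in the low-risk tertile, ≤4 in the intermediate one and ≤3 in the high-risk one.

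On timing, eligibility requires "hospital admission within 24 hours of injury" (section 5.1). Randomisation follows "Once reaching a Hb ≤ 100 g/L and after a site investigator has confirmed eligibility" (section 3.1). The same section adds: "The trial intervention is initiated within 3 hours in patients meeting the threshold for transfusion in their respective group". The SAP gives no minimum interval between injury and randomisation.

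**The concern.** A variable that decides what counts as a bad outcome should be fixed before treatment can act on it. The stated CT window can stay open after randomisation, and CT is the only score input for which the text allows this. A later, worse scan raises predicted risk and can move the patient up a tertile, where GOSe 5 (low to intermediate) or GOSe 4 (intermediate to high) stops counting as unfavourable.

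If the strategies affect early lesion progression, or if repeat scanning differs by arm in this open-label trial, the arm with more late, worse scans is judged against more lenient cut-offs. The direction is not fixed. If liberal transfusion worsened early CT findings, the bias would favour it; if it prevented progression, the bias would count against it.

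The same CT items are covariates in the additional proportional-odds and GOSe ≤4 Poisson models (section 6.2.1.3) and in the main secondary models (section 6.2.2.1). Those models could therefore adjust for a post-randomisation variable.

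**Working it through.** **1. The plan's own figures (scale only).** Section 3.3: 40% v 30%, 80% power, 5% type I error, taken as two-sided, 1:1.

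n per arm = [1.96·√(2·0.35·0.65) + 0.8416·√(0.40·0.60 + 0.30·0.70)]² / 0.10² = (1.322 + 0.565)² / 0.01 ≈ 355.9, so 356 per arm and **712** in total, as stated. Section 3.5: 712 / 0.98² = 741.4, so **742**, as stated. Neither figure depends on the CT rule.

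**2. Can the overlap occur?** Take a patient randomised 8 hours after injury in the liberal arm, whose threshold equals the entry haemoglobin of ≤100 g/L. Treatment can start by 8 + 3 = 11 hours. A worse scan at 20 hours falls inside the 24-hour window, and the rule would use it. Nothing in the SAP excludes this sequence.

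**3. How many patients?** The injury-to-randomisation row in Appendix 2 is an empty shell, so every input here is an assumption:

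| Input | Low | High |
|---|---|---|
| Randomised within 24 h of injury | 5% | 40% |
| Of those, later worse scan inside the window | 10% | 30% |
| Of those, change of tertile | 20% | 33% |
| At the GOSe level where the cut moves | 12% | 12% |

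- Low: 0.05 × 0.10 × 0.20 = 0.1% re-banded; × 742 = 0.7 patients; × 0.12 = 0.1 outcomes.
- High: 0.40 × 0.30 × 0.33 = 4.0% re-banded; × 742 = 29 patients; × 0.12 = 3.5 outcomes.

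**4. How much bias?** Only the between-arm difference in re-banding biases the comparison.

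- Equal re-banding in both arms: no differential bias.
- High inputs, with 30% v 15% later worse scans by arm: 0.40 × 0.15 × 0.33 × 0.12 = 0.24 percentage points.
- High inputs, all re-banding in one arm: 0.40 × 0.30 × 0.33 × 0.12 = 0.48 percentage points.

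**5. Effect on the test.** SE at p = 0.40 with 356 per arm: √(2 × 0.40 × 0.60 / 356) = 3.67 points. Shift = 0.48 / 3.67 ≈ 0.13 SE. If treatment altered CT but not GOSe, two-sided type I error would be [1 − Φ(1.96 − 0.13)] + Φ(−1.96 − 0.13) ≈ 0.034 + 0.018 = **0.052**, against a nominal 0.05.

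**6. Beyond those ranges.** Write the bias as f × d × g: share randomised within 24 hours, between-arm difference in the probability of moving up a tertile, and probability of sitting at the moving GOSe level. Then 0.6 × 0.10 × 0.20 gives 1.2 points (type I error 0.062), and 1.0 × 0.10 × 0.20 gives 2.0 points (0.085). These cases need 60% to 100% of patients randomised within 24 hours.

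**7. After the fix.** With pre-randomisation scans only, this route to bias closes and the bias is 0.

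**The case against.** The best defence is that the effect is small and may be negligible. Randomisation also needs confirmed eligibility, so it need not be immediate once haemoglobin falls. Appendix 2 reports injury-to-randomisation time in days and lists many events before randomisation, including intracranial pressure monitoring, craniectomy and haematoma evacuation. This suggests that a substantial course before randomisation was expected. If most patients are randomised after 24 hours, little is left of the problem. That stands as a limit on size. It does not exclude randomisation inside 24 hours, and the rule gives no protection when it happens.

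The plan also has analyses free of CT: a chi-square test on GOSe ≤4 and unadjusted analyses of all secondary outcomes. They are useful checks. However, the chi-square test addresses a different endpoint, so a discrepancy with the main analysis would not show that the CT rule caused it.

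Three stronger readings are tempting and not supported:

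- **The main primary model adjusts for CT.** It does not. Sections 6.2 and 6.2.1.1 and the Table 1 footnote give sex and site only. CT reaches the main analysis only through the tertiles.
- **Unblinded reading contaminates the score.** Appendix 3 opens its safeguard with "Given that the local research teams were unblinded to transfusion strategies", then provides two central assessments by investigators blinded to allocation and outcome, the later one final. That answers the reading question. It does not address when the scan was taken, a real treatment effect on the lesion, or arm-dependent repeat scanning.
- **A material bias has been shown.** It has not. No figure in the SAP shows how often the overlap occurs.

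**Conclusion.** The point holds as a gap in definition. For patients randomised within 24 hours of injury, the SAP allows a post-randomisation scan to set the risk tertile and hence the GOSe cut-off, and to enter the additional and main secondary models as a covariate.

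The differential bias is likely below about 0.5 percentage points against a target of 10, with type I error near 0.052 at that upper value, and it is nil if re-banding is equal across arms. This rests on the assumed ranges above (at most 40% randomised within 24 hours). It would be larger only if early randomisation were much more common and re-banding differed substantially by arm. This is a cheap improvement to the rule and not a threat to the trial's conclusion. The sample sizes of 712 and 742 are unaffected.

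**What to change.** In section 6.1.1 and the CT footnote of Appendix 2, with Appendix 3 to match, define the CT input as *the worst CT within the first 24 hours after injury and before randomisation*. Use that one rule for the tertiles and for the CT covariates. It should say worst, not last: the two can differ, for example after a haematoma evacuation before randomisation, and a last scan may fall outside the 24 hours. Report how many patients were randomised within 24 hours of injury and, by arm, how many worst scans were dated after randomisation.

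If re-reading is impractical, keep the current rule for the main analysis and add a sensitivity analysis of the primary outcome with tertiles recomputed from pre-randomisation scans only. The site readings described in Appendix 3 could supply the values where they exist for the earlier scan.

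The cost is a check of scan time against randomisation time and a few re-reads by the existing adjudicators. Appendix 3 describes adjudication in the past tense, so this means reopening a small number of cases.
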